12.1.3.6 DOSE MODIFICATION FOR OTHER ADVERSE EVENTS

For all Grade ≥ 3 treatment-emergent AEs (other than the hepatic and pancreatic AEs described in [sections 12.1.3.2](#) and [12.1.3.3](#)), study drug should be dose-reduced (if at the 0.3 mg/kg daily dose) or permanently discontinued (if at the 0.1 mg/kg daily dose).

All AEs should be recorded as AEs per [Section 12.1](#) and [Section 12.3](#).

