6.5 DOSE JUSTIFICATION FOR STUDY

6.5.1 RATIONALE FOR STARTING DOSE (0.1 MG/KG)

The 0.1 mg/kg/day dose was selected to satisfy the following criteria:

- Predicted steady state drug levels for the nominal as well as the maximum dose (based on weight bracketing) are below the no observed adverse effect level (NOAEL) values for C_{max} and AUC_{0-24} observed in toxicology studies (Table 2)

[figure not shown]
- Predicted steady state C_{max} and AUC_{0-24} are not expected to exceed the values observed during the Phase 1 RA101495-1001 MD study in healthy volunteers (Table 2)
- Inhibition of hemolysis is expected to be maintained at $\geq 90\%$ at all times (following a loading dose of 0.3 mg/kg; see [Section 6.5.2](#)). This prediction is supported by overlaying the expected RA101495 plasma concentrations at steady state, with the PK/PD relationship obtained from Phase 1 studies in healthy volunteers ([Figure 7](#)). Adequate and sustained control of hemolysis is a key component of both efficacy and safety in PNH. In this disease, even a modest transient decrease in complement blockade can lead to immediate “breakthrough” intravascular hemolysis and recrudescence of severe PNH symptoms. This consideration is particularly important with respect to the potential for missed doses.

Table 2 Experimental and Predicted PK Values for RA101495 in Humans

Pharmacokinetic Parameter	Statistic	RA101495 (2 mg/kg) NOAEL NHP	RA101495 (0.2 mg/kg) QDx7; Day 7 Human (SD)	RA101495 (0.1 mg/kg) Steady State Prediction in Human	
				Nominal (Minimal) 0.1 mg/kg QD	Maximum dose* 0.14 mg/kg QD
C_{max} ($\mu\text{g/mL}$)	Mean	33.8	7.29 (0.66)	6.57	7.12
AUC_{0-24} ($\text{h}\cdot\mu\text{g/mL}$)	Mean	573	151.3 (12)	141.5	152.8

*Indicates the potential maximum dose received by patients due to weight bracketed dosing

Figure 7 Predicted PK and PD Effects Resulting From Weight-Bracketed Dosing of RA101495 (0.1mg/kg daily)

[figure not shown]

Note: Predicted plasma concentration range (blue lines) resulting from weight-bracketed dosing of RA101495 at 0.1mg/kg daily and expected PD effect (% hemolysis).

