8.1.1 RATIONALE FOR STUDY DESIGN

No Comparator

The current study in PNH subjects is designed as an open-label study and does not include a placebo group. Given the severity of the disease, and the availability of an approved treatment, it is considered inappropriate to administer a placebo to subjects with PNH.

Dose Selection and Presentation

The starting dose selected for the study is 0.1 mg/kg (following a loading dose of 0.3 mg/kg). This dose level of RA101495 is anticipated to achieve and maintain ≥90% sustained inhibition of hemolysis based on the Phase 1 healthy volunteer study and pharmacokinetics and pharmacokinetic modeling (see [Section 6.5 Dose Justification](#)). A second, higher dose level (0.3 mg/kg) will be available for those subjects who do not adequately respond to the starting dose (i.e. with LDH ≥1.5xULN).

Dose presentation and administration of RA101495 will be determined by a target weight-based approach, accomplished using fixed-dose-by-weight brackets supporting a weight range of 43 to 109 kg. This method of dosing will insure that no subject receives a sub-therapeutic dose.

Avoidance of sub-therapeutic doses is critically important in PNH to minimize the risk of breakthrough hemolysis.

Primary Efficacy Endpoint

The efficacy endpoint for the study is the change in LDH from baseline to the primary evaluation period (mean of values at the Week 6, Week 8, Week 10, and Week 12 visits). LDH has been selected as the primary endpoint because LDH is an enzyme that catalyzes the conversion of lactate to pyruvic acid and vice versa, highly abundant in erythrocytes and is a well-established marker of intravascular hemolysis in PNH. Since the approval of eculizumab, LDH has emerged as a clinically accepted marker for monitoring the response to therapy, and for identifying subjects experiencing breakthrough hemolysis [Soliris® 2016; Soliris® 2015]. In subjects approaching the end of the 14-day eculizumab dosing interval, there is a close correlation between the return of complement activity, clinical manifestations of breakthrough intravascular hemolysis, and elevations in LDH [Hill, 2005].

Rationale for the study population and the definition of inadequate response

[figure not shown]

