10.1.2.1 DOSE ESCALATION

After 2 weeks of treatment with RA101495 at 0.1 mg/kg, if a subject has not achieved an adequate response (defined as an LDH <1.5xULN), the dose should be escalated to 0.3 mg/kg daily. Dose escalation may proceed only if no severe (i.e. Grade ≥3) or serious treatment-emergent adverse events are reported at the 0.1 mg/kg dose.

For subjects who have a dose increase to 0.3 mg/kg, samples for PK and PD should be collected at pre-dose of the first day of the new dose, then at scheduled visits per the Time and Events Table (Table 1).

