12.1.3.2 HEPATIC ADVERSE EVENTS

All subjects should be monitored for signs and symptoms of hepatic or biliary dysfunction. Liver function tests (LFTs) (ALP, ALT, AST, GGT, Direct Bilirubin and Indirect Bilirubin) are monitored weekly for the first 4 weeks followed by every 2 weeks during the study. The following guideline is provided:

- In subjects with isolated ALT or AST elevation $>2xULN$ with no other explanation for the elevation(s), contact the medical monitor to review the case details and determine if the subject should continue study treatment, reduce dose, or discontinue study treatment. The subject should be monitored until the elevated enzymes return to less than or equal to $2xULN$.
- In subjects with isolated direct bilirubin elevation $>2xULN$ with no other explanation for the elevation(s), contact the medical monitor to review the case details and determine if the subject should continue study treatment, reduce dose, or discontinue study treatment. The subject should be monitored until the direct bilirubin return to less than or equal to $2xULN$.
- Subjects with isolated ALT or AST elevations $>3xULN$ concurrently with direct bilirubin elevation $>2xULN$ and a normal ALP with no other explanation for the elevation should be permanently discontinued. The medical monitor should be contacted as soon as possible to review the case. The subject should be monitored until the elevated enzymes return to Grade 1 National Cancer Institute Common Terminology Criteria for Adverse Events (NCI CTACE Version 4.03) or lower, and the direct bilirubin is less than or equal to $2xULN$.

All AEs should be recorded as AEs per [Section 12.1](#) and [12.3](#).

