12.1.3.3 PANCREATIC ENZYME ELEVATIONS

Subjects should be monitored during the study for symptoms of pancreatitis or cholecystitis. Pancreatic enzymes (amylase and lipase) are monitored weekly for the first 4 weeks followed by every 2 weeks during the study.

- In subjects with elevations of amylase or lipase to NCI CTCAE (Version 4.03) Grade 3 ($>2xULN$) study drug should be dose-reduced (if at the 0.3 mg/kg daily dose or permanently discontinued (if at the 0.1 mg/kg daily dose). The subject should be monitored until amylase and /or lipase returns to Grade 1 or lower. The medical monitor should be contacted to review the case.

- In subjects with elevations of amylase or lipase to NCI CTCAE (Version 4.03) Grade 4 (>5xULN) study drug should be permanently discontinued. The subject should be monitored until amylase and /or lipase returns to Grade 1 or lower. The medical monitor should be contacted to review the case

All AEs should be recorded as AEs per [Section 12.1](#) and [Section 12.3](#)

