12.2.2 CAUSALITY

The causal relationship of the AE to study medication will be assessed by both the investigator and the Sponsor. The assessment of causal relationship to study drug should be evidence-based, and not based on the premise that all AEs are causally related to study drug until proven otherwise. Default categorization of ‘related’ without supportive evidence for a causal relationship to study drug is generally uninformative and does not contribute to understanding of the safety profile of the drug with respect to the intended population.

Examples of evidence that would suggest a causal relationship between the drug and the AE include occurrence of an AE that is known to be strongly associated with drug exposure (e.g. injection site reaction), or an AE that is otherwise uncommon in the study population. Lack of efficacy of study drug, in isolation, leading to unmasking of underlying symptoms and signs of disease, should not be considered evidence of relatedness.

The causal relationship of each AE is assessed using a binary system with all AEs classified as either ‘related’ or ‘not related’.

Related: There is ‘reasonable possibility’ that the drug caused the AE. The AE follows a reasonable temporal association from the time of study drug administration. There is supportive evidence to suggest a possible causal relationship, irrespective of the degree of certainty, between the observed AE and the study drug. There is no alternative more likely explanation for the AE. Lack of study drug efficacy is not considered, by itself, to be evidence of relatedness.

Not Related: Lack of a reasonable temporal association from the administration of the study drug and the occurrence of the AE. There is evidence of an alternative explanation that is more likely as a cause of the AE.

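### Section 12.1.3.6 has no exception for Grade ≥3 events caused by lack of efficacy, so Grade ≥3 hemolysis leads to less drug or to none

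*Protocol*

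**What the plan says.** **Dose modification.** Protocol Section 12.1.3.6 covers every Grade ≥3 treatment-emergent event except those handled in 12.1.3.2 (hepatic) and 12.1.3.3 (pancreatic). For these, "study drug should be dose-reduced (if at the 0.3 mg/kg daily dose) or permanently discontinued (if at the 0.1 mg/kg daily dose"). The section has no condition on cause and provides for no medical monitor review.

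**Escalation.** Section 10.1.2.1 sets the rule that applies once two weeks on the starting dose have passed: "if a subject has not achieved an adequate response (defined as an LDH <1.5xULN), the dose should be escalated to 0.3 mg/kg daily". It adds a bar: "Dose escalation may proceed only if no severe (i.e. Grade ≥3) or serious treatment-emergent adverse events are reported at the 0.1 mg/kg dose". Section 10.1.3 gives only two daily doses, 0.1 and 0.3 mg/kg, and prohibits eculizumab from Day 1 onward.

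**Loss of complement blockade.** Section 6.5.1 warns that even a small, brief loss of blockade can bring on "intravascular hemolysis and recrudescence of severe PNH symptoms".

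**Lack of efficacy.** Section 12.2.2 takes up "Lack of efficacy of study drug, in isolation, leading to unmasking of underlying symptoms and signs of disease" and says that this is not evidence of relatedness. It goes no further than causality.

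**Case-by-case handling elsewhere.** For isolated transaminase or direct bilirubin elevations, Section 12.1.3.2 has the site consult the medical monitor to "determine if the subject should continue study treatment, reduce dose, or discontinue study treatment".

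**The concern.** The rule treats every Grade ≥3 event as a reason to give less drug. For toxicity that is the right direction. For an event caused by too little complement inhibition it is the wrong one.

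A subject is on 0.3 mg/kg daily only because LDH was not below 1.5×ULN on 0.1 mg/kg. If that subject then has Grade ≥3 hemolysis, the protocol asks for a return to the dose already judged inadequate for that subject, while eculizumab is not allowed on study.

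At 0.1 mg/kg the same event has two consequences. Section 12.1.3.6 stops the drug permanently, and Section 10.1.2.1 closes the route to 0.3 mg/kg. Yet Section 8.1.1 presents the higher dose as the answer to this problem: "A second, higher dose level (0.3 mg/kg) will be available for those subjects who do not adequately respond to the starting dose". A subject who is stopped does not complete the 12-week Treatment Period, so leaves the Efficacy Evaluable Population (13.2.2), and does not meet the completion condition for the extension study (8.1).

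**Working it through.** **1. Does hemolysis fall under the rule?** Section 13.3.4.1 counts as treatment-emergent an event that is new after treatment start or that worsens after it. New or worsened hemolysis can therefore qualify. Section 12.2.2 affects only the relatedness label, and 12.1.3.6 does not use relatedness. The rule applies once such an event is graded 3 or higher. The CTCAE grades for hemolysis are in a separate manual (12.2.1), so how often hemolysis would reach Grade 3 is not known here.

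**2. Size of the cut.** With two daily doses, a reduction from 0.3 mg/kg means 0.1 mg/kg. From the syringe contents in Table 3, cut = 1 − (0.1 mg/kg syringe)/(0.3 mg/kg syringe):

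| Weight (kg) | Calculation | Cut |
|---|---|---|
| 43 to <56 | 1 − 6/16.6 | 63.9% |
| 56 to <61 | 1 − 6/23 | 73.9% |
| 61 to <77 | 1 − 8.8/23 | 61.7% |
| 77 to <88 | 1 − 8.8/32.4 | 72.8% |
| 88 to <109 | 1 − 12.4/32.4 | 61.7% |

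The range is 62% to 74%. This is dose, not exposure. With the half-life of 161.9 h in Section 6.3, the share of the excess exposure left after 7 days is 0.5^(168/161.9) = 0.49, and after 14 days 0.5^(336/161.9) = 0.24.

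**3. Is there a way back to 0.3 mg/kg?** Sections 8.1 and 10.1.2.1 set no once-only limit on escalation. The bar counts only events reported at 0.1 mg/kg, so an event at 0.3 mg/kg does not trip it. Read literally, a reduced subject whose LDH is again not below 1.5×ULN should be escalated again. Nothing in that protocol rule requires the event to have resolved or the medical monitor to agree. SAP Section 2.2 does mention a safety evaluation by the investigator and the medical monitor before escalation. However, the SAP cites protocol version 1.1 of 20 October 2016, and the current protocol is Amendment 1 of 17 January 2017.

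Example, assuming escalation on Day 15, reduction on Day 29 and a fresh two weeks at 0.1 mg/kg: return is possible from Day 29 + 14 = Day 43, after 14 days at the lower dose (Days 29 to 42). If the site read the silence as no return, the figure would be 84 − 29 + 1 = 56 days. The text does not say which applies.

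**4. Effect on the primary mean.** The plan's own figure first: SE = SD × √(2(1 − ρ)/n) = 443 × √(2 × 0.2/6) = 114.4 U/L, which agrees with the stated value of about 114. If the dose change moves one subject's primary-period LDH by 100 U/L (an assumed amount), the mean moves by 100/6 = 16.7 U/L at n=6, or 100/8 = 12.5 U/L at n=8. At n=6 that is 16.7/114.4, about 15% of the standard error.

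**The case against.** **Cause-blind reduction is ordinary caution.** Earlier repeat dosing was 0.2 mg/kg for 7 days in four treated healthy volunteers (6.3), so 0.3 mg/kg daily exceeds any earlier repeated human dose. With 6 to 8 subjects and no control arm, attribution is unreliable. This stands for events other than lack of efficacy, including unrelated events and injection site reactions. The pancreatic rule in 12.1.3.3 ("study drug should be dose-reduced (if at the 0.3 mg/kg daily dose or permanently discontinued") uses the same logic and is not at issue.

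**The sponsor does not expect severe hemolysis.** Section 6.4 expects daily dosing to remove end-of-cycle breakthrough, and 6.5.3 models inhibition above 95% on 0.1 mg/kg. This stands as a point about frequency. It does not justify the direction of the rule when such an event occurs, and the dose escalation step exists because some subjects may respond inadequately.

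**Dose is not effect.** In Table 2, 40% more dose (0.10 to 0.14 mg/kg) raises predicted AUC by only 152.8/141.5 − 1 = 8%. This also stands: the cut in complement inhibition could be much smaller than 62% to 74%. The subject's own LDH at 0.1 mg/kg is the better evidence that the lower dose was not enough.

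**There are ways around the rule.** The wording is advisory, and Section 14.3 allows departures for immediate hazards and gives a medical monitor route for individual deviations. That softens the consequence, but it leaves the right action to be handled as a deviation.

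**A stronger reading that the documents do not support.** A reader might infer that a reduced subject is held at 0.1 mg/kg until Day 84, with withdrawal as the only alternative. Section 8.1.1 merely names a second dose level. The single escalation date in SAP Section 3.7 and the PK table titles in the post-lock SAP amendment describe reporting and do not restrict dosing. The literal escalation rule permits a return.

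**Conclusion.** The concern holds in a narrow form. Outside the hepatic and pancreatic rules, 12.1.3.6 makes no exception for lack of efficacy. It therefore directs a cut of 62% to 74% in dose for Grade ≥3 hemolysis at 0.3 mg/kg. At 0.1 mg/kg it directs permanent discontinuation, with escalation barred as well. Separately, the protocol is silent on return to 0.3 mg/kg after a reduction, and its literal LDH rule would allow a return with no stated check on resolution.

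This rests on three things: hemolysis is recorded as a new or worsened adverse event, it is graded 3 or higher, and the site follows the rule as written. Frequency cannot be estimated from the documents, and few subjects would be affected. The primary mean would barely move. This is a patient safety point with a cheap remedy, and it does not threaten the trial's conclusions.

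**What to change.** Add to Section 12.1.3.6, with a cross-reference in 10.1.2.1:

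> *A Grade ≥3 event that the investigator and the medical monitor attribute to lack of efficacy (12.2.2) does not by itself require reduction from 0.3 mg/kg or discontinuation at 0.1 mg/kg, and does not by itself bar escalation to 0.3 mg/kg.*

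The bar in 10.1.2.1 also covers serious events, so the cross-reference should say whether the exception still applies when such an event is also serious.

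As a secondary clarification, state that return to 0.3 mg/kg after a safety reduction requires resolution of the event and the medical monitor's agreement. Keep the cause-blind reduction for all other Grade ≥3 events.

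The cost is two sentences and a cross-reference, with no added visits, samples or subjects. The downside is medical monitor time and reliance on attribution for this one class of event.

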12.2 EVALUATION AND CLASSIFICATIONS

12.2.1 SEVERITY

The investigator should determine the severity of the reported AE by using the NCI-CTCAE (Version 4.03). These criteria will be provided in a separate manual.

For any reported AE not described in the NCI-CTCAE, the following guidelines must be considered for severity evaluation:

Adverse Event Severity

Mild	Symptom(s) barely noticeable to subject or does not make subject uncomfortable; does not influence performance or functioning; prescription drug not ordinarily needed for relief of symptom(s).
Moderate	Symptom(s) of a sufficient severity to make subject uncomfortable; performance of daily activity is influenced; subject is able to continue in study; treatment for symptom(s) may be needed.
Severe	Symptom(s) cause severe discomfort; symptoms cause incapacitation or significant impact on subject's daily life; severity may cause cessation of treatment with study treatment; treatment for symptom(s) may be given

Adverse Event Severity

Mild Symptom(s) barely noticeable to subject or does not make subject uncomfortable; does not influence performance or functioning; prescription drug not ordinarily needed for relief of symptom(s). and/or subject hospitalized.

12.2.2 CAUSALITY

The causal relationship of the AE to study medication will be assessed by both the investigator and the Sponsor. The assessment of causal relationship to study drug should be evidence-based, and not based on the premise that all AEs are causally related to study drug until proven otherwise. Default categorization of ‘related’ without supportive evidence for a causal relationship to study drug is generally uninformative and does not contribute to understanding of the safety profile of the drug with respect to the intended population.

Examples of evidence that would suggest a causal relationship between the drug and the AE include occurrence of an AE that is known to be strongly associated with drug exposure (e.g. injection site reaction), or an AE that is otherwise uncommon in the study population. Lack of efficacy of study drug, in isolation, leading to unmasking of underlying symptoms and signs of disease, should not be considered evidence of relatedness.

The causal relationship of each AE is assessed using a binary system with all AEs classified as either ‘related’ or ‘not related’.

Related: There is ‘reasonable possibility’ that the drug caused the AE. The AE follows a reasonable temporal association from the time of study drug administration. There is supportive evidence to suggest a possible causal relationship, irrespective of the degree of certainty, between the observed AE and the study drug. There is no alternative more likely explanation for the AE. Lack of study drug efficacy is not considered, by itself, to be evidence of relatedness.

Not Related: Lack of a reasonable temporal association from the administration of the study drug and the occurrence of the AE. There is evidence of an alternative explanation that is more likely as a cause of the AE.

12.3 RECORDING, REPORTING, AND MONITORING

12.3.1 RECORDING AND REPORTING

The investigator must make every effort to properly evaluate all information relevant to the reported AE in such a way that a diagnosis can be confidently made and reported. For example, it is preferable to report “pneumonia” as the AE rather than its symptoms (e.g. “rales” or “fever”) as separate AEs.

When recording and/or reporting AEs or SAEs, the following elements must be included:

- the fulfilled criteria for seriousness as presented in [Section 12.1.2](#)

- the severity of the event as defined in [Section 12.2.1](#)
- the relationship of the event to study treatment as defined in [Section 12.2.2](#)

Actions taken in relation to the AE will be recorded as drug discontinued, drug interrupted, dose reduced, dose increased, concomitant medication, other action (e.g. diagnostic testing), or no action. Any medication given to treat the AE will be recorded separately in the concomitant medication list of the eCRF.

The outcome of the AE will be recorded as date ended, ongoing, or resulting in death with date of death.

12.3.1.1 ADVERSE EVENTS

Pre-existing conditions that are detected prior to administration of the first dose of study drug will be recorded as part of medical history. For all subjects, the AE reporting period will start with the first administration of study drug on Day 1 and will end with the final study visit, after which no new AEs are to be reported. When possible, ongoing AEs assessed as related to the study drug will be followed until resolved or stabilized.

The subjects will be monitored throughout the study for any AEs, including abnormal, clinically significant laboratory values, clinically significant findings at vital signs measurements, spontaneous reports by study subjects, and observations by the study personnel. Adverse events will be coded using MedDRA after the eCRFs have been monitored and signed by the investigator.

All AEs will be recorded in the eCRF. The investigator will assess and record any AE in detail including the date and time of onset, event diagnosis (if known) or sign/symptom, severity, time course (end date or ongoing), relationship of the AE to study drug, and any action(s) taken. All AEs should be reported separately (i.e. 1 record per event). Reporting of AEs is event-based (i.e. an ongoing event will not be closed until resolved or at the end of study). For the AE description, a diagnosis is preferred over symptoms. If no diagnosis can be made, each symptom will be reported as a separate AE. Abbreviations should be avoided. Descriptive words should be used for ongoing conditions as applicable (e.g. exacerbation of herpes genitalis or worsening of eczema).

